### **8.1.2. Methodology for Safety Endpoints**

The denominators for all proportions will be the number of subjects in the vaccine group, except where noted.

All CIs for proportions will be 2-sided 95% intervals, obtained using the Clopper-Pearson method. There will be no adjustments for multiplicity.

#### **8.1.2.1. Adverse Events and Serious Adverse Events**

AEs will be summarized using 3-tier methodology.

Tier 1 includes all AEs of special interest. These may be determined by vaccine knowledge, experience with similar vaccines, and results from Phase 1 and 2 studies. For such AEs, incidence proportions, the difference between vaccine groups in proportions, 95% CI on the difference, 2-sided p-value on the difference, and graphical displays of the differences will be compiled. Currently, no Tier 1 events are specified for the *S aureus* studies, as there are no specific AEs considered by Pfizer to have been of sufficient clinical importance to identify them as Tier 1 events during safety reviews performed across the early-phase studies. Tier 1 AEs, if any, will be specified by the sponsor in the safety review plan under separate cover.

Tier 2 includes all AEs with  $\geq 1\%$  incidence in either vaccine group in either the preoperative period or the postoperative (Days 1-42) period. For such AEs, incidence proportions, the differences between vaccine groups in proportions, and 95% CIs on the differences will be compiled.

Tier 3 includes all remaining AEs. For such AEs, only incidence proportions will be compiled.

[figure not shown]
The CIs on the differences between vaccine groups for Tier 1 will be computed using the Chan and Zhang method. The CIs on the differences between vaccine groups for Tier 2 may use the Miettinen and Nurminen method. This method is an approximation and, therefore, computationally faster. The approximation is acceptable for Tier 2 because these analyses are exploratory.

All risk differences will be calculated as SA4Ag minus placebo.

Risk differences will be plotted, along with 95% CIs, for Tier 1. p-Values will be included in the plot. Figure 1 shows an example.

The 3-tier methodology will not be used for presurgery AEs, because these AEs will be summarized as rates. The number of days of exposure will be calculated as the date of the index surgery minus the date of vaccination, plus 1, which counts both the day of vaccination and the day of surgery. Exposure will be the discharge day minus the vaccination day, plus 1, for subjects without surgery. Total exposure, in days, will be compiled for both vaccine groups. Counts will be fit to a Poisson regression, with total exposure as an offset. Total exposure will be log transformed.

The proportions of deaths will be compiled by vaccine group, using sample size as the denominators. Vaccine groups will be compared using the Fisher exact test, 2-sided, by preferred term, by system organ class, and with all terms combined. Deaths will be further categorized as associated or not associated with *S aureus* infection, as determined by the EAC. The proportions of deaths associated with *S aureus* will be compiled by vaccine group, but the denominators will be the number of deaths. Vaccine groups will be compared using the Fisher exact test, 2-sided, by preferred term, by system organ class, and with all terms combined.

Statistical analyses for AEs are summarized in [Section 8.2.2.1](#).

#### **8.1.2.2. Methodology for Multiple-Organ Failure**

The denominators for organ systems that failed and subjects meeting MOF criteria will be all subjects in the safety population. Vaccine groups will be compared using the Fisher exact test, 2-sided, for each organ system. These p-values will include subjects with 2 or more failed systems, so they should be interpreted cautiously.

Subjects with MOF will be split into 2 categories: “associated with infection” (subdivided as “PDI” or “non-PDI [other infection]”) and “not associated with infection” (subdivided as “other [not an infection]” and “unknown”). The denominators will be all subjects in the safety population in order to obtain the absolute risk of subjects’ having MOF associated with infection. The Fisher exact test, 2-sided, will be used to compare vaccine groups in association with infection.

Subjects with MOF associated with infection will be further split into the categories “PDI” and “non-PDI (other infection).” The denominators will be all subjects in the safety

population. Vaccine groups will be compared in both the PDI and non-PDI subcategories with the Fisher exact test, 2-sided.

The subcategories PDI and non-PDI will each be further split into “microbiologically confirmed *S aureus* infection,” “microbiologically confirmed non-*S aureus*,” and “non-microbiologically confirmed infection.” “Non-microbiologically confirmed infection” will be further split into “negative” and “not done.” The denominators will be all subjects in the safety population. Vaccine groups will be compared in each level within each subcategory using the Fisher exact test, 2-sided.

Subjects with MOF not associated with infection will be further split into the categories “other” and “unknown.” The denominators will be all subjects in the safety population. Vaccine groups will be compared in the other and unknown subcategories with the Fisher exact test, 2-sided.

Site is not proposed as a stratification factor in any analyses because of the expected sparseness of MOFs.

Statistical analyses are summarized in [Section 8.2.2.2](#).

### **8.1.2.3. Methodology for Local Reactions and Systemic Events After Vaccination**

Binary endpoints (eg, any redness on Days 1-10 after vaccination) will be summarized with proportions by vaccine group. Two-sided 95% CIs will be compiled for all proportions. Vaccine groups will be compared using method of Miettinen and Nurminen.

The number and proportion of subjects with indicated local reaction or systemic event on each day will be compiled by vaccine group, but vaccine groups will not be statistically compared.

Vaccine groups will be compared in duration and onset using the Mann-Whitney test, 2-sided.

Vaccine groups will be compared in baseline assessments of fatigue, headache, muscle pain, and joint pain using the Fisher exact test, 2-sided.

NNH will be calculated for both any local reaction and any systemic event. A 95% CI will be obtained for each NNH by obtaining a 2-sided 95% CI on the difference in proportions using the method of Chan and Zhang, then reciprocating the upper and lower limits. The difference in proportions is defined as SA4Ag minus placebo.

1. If the difference in proportions and both confidence limits are less than zero, then the results will be presented as number needed to benefit (NNB) = xx.x (xx.x, xx.x), with the negative signs omitted.
2. If the difference in proportions and both confidence limits are greater than zero, then the results will be presented as NNH = xx.x (xx.x, xx.x).

3. If the CI brackets zero, then the results will be presented as NNB (if negative) or NNH (if positive) = xx.x (NNH = xx.x, NNH = xx.x), with any negative signs omitted.

Baseline assessments will be summarized by proportion of any response (ie, mild, moderate, or severe) and by proportion that are moderate or severe. Vaccine groups will be compared using the Fisher exact test, 2-sided.

Statistical analyses for local reactions and systemic events are summarized in [Section 8.2.2.3](#).

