3. If the CI brackets zero, then the results will be presented as NNT (if negative) or NNH (if positive) = xx.x (NNT = xx.x, NNH = xx.x), with any negative signs omitted.
4. If the difference in proportions is exactly zero, then the estimated NNT will be presented as  $NNT = \infty$ .

Statistical analyses for efficacy are summarized in [Section 8.2.1](#).

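### SAP 8.1.2.3, rule 3: when the interval crosses zero, both limits of the number needed to harm are labelled NNH, so the benefit-side limit is printed as harm

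*SAP*

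**What the plan says.** The Methodology for Local Reactions and Systemic Events After Vaccination (SAP 8.1.2.3) states that "NNH will be calculated for both any local reaction and any systemic event". The interval comes from "obtaining a 2-sided 95% CI on the difference in proportions using the method of Chan and Zhang", "then reciprocating the upper and lower limits". The sign convention is explicit: "The difference in proportions is defined as SA4Ag minus placebo". A positive difference therefore means more reactions on vaccine and a negative one means fewer.

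Three display rules follow:

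- Rule 1, estimate and both limits negative: "presented as number needed to benefit (NNB) = xx.x (xx.x, xx.x), with the negative signs omitted".
- Rule 2, estimate and both limits positive: the result is shown as NNH, with two unlabelled limits.
- Rule 3, interval includes zero: the estimate is called NNB or NNH according to its sign, followed by "xx.x (NNH = xx.x, NNH = xx.x), with any negative signs omitted".

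The corresponding efficacy rule in SAP 8.1.1 ends "xx.x (NNT = xx.x, NNH = xx.x), with any negative signs omitted". The number-needed-to-harm row of SAP Table 20 names the two endpoints and the reciprocal method but gives no labelling rule of its own, so 8.1.2.3 governs the output.

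**The concern.** Rule 3 operates only when one limit is below zero and the other above. After reciprocation, one printed number belongs to the benefit side and the other to the harm side. The rule gives both the harm label. Because the sign is also omitted, the label is the only thing that says which side a limit is on, and for one limit it is wrong.

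Local reactions and systemic events in the 10 days after vaccination are primary safety endpoints (Protocol 2.2.1). A programmer who follows the SAP literally would build the wrong label into the table shell. An inconclusive comparison would then be printed with no benefit-side limit identified as such.

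**Working it through.** The SAP states no numerical NNH, so there is no figure to reproduce. The check applies the rules as written.

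**Signs alone.** Let d be the difference and L, U its 95% limits, with L < 0 < U.

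- 1/U is positive, so it is an NNH by rule 2.
- 1/L is negative, so its absolute value is an NNB by rule 1.
- Rule 3 prints 1/|L| as NNH. That label is wrong for every interval to which rule 3 applies, whatever the rates, sample size or interval method.

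**What the reader would see.**

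- If d < 0, the estimate is labelled NNB and both limits NNH, so the line contradicts itself.
- If d > 0, then d < U gives 1/d > 1/U. The printed estimate also exceeds 1/|L| whenever |L| > d, and it then lies above both printed limits. If |L| < d, it lies between them, and nothing in the numbers reveals the error.

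**Illustration.** The reaction rates are assumptions; the documents give none for this trial. About 6,000 planned subjects randomized 1:1 (SAP 2.1) would be 3,000 per arm. SAP 8.1.3.5 records that enrollment stopped in December 2018 after futility was met, so 1,500 per arm was run as well. Score-type limits stand in for Chan and Zhang. They agreed with Wald limits to within 0.0001, and the label does not depend on the method.

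For 31% against 30% with 3,000 per arm:

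- d = 0.31 − 0.30 = 0.01
- SE = √[(0.31 × 0.69 + 0.30 × 0.70)/3000] = √(0.4239/3000) = 0.0119
- half-width = 1.96 × 0.0119 = 0.0233
- limits −0.0133 and 0.0333
- reciprocals, from unrounded limits: 1/d = 100.0, 1/L = −75.2, 1/U = 30.0

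Three cases at 3,000 per arm:

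| SA4Ag vs placebo | Limits of d | Rule 3 as written | Negative limit relabelled |
|---|---|---|---|
| 31% vs 30% | −0.0133, 0.0333 | NNH = 100.0 (NNH = 75.2, NNH = 30.0) | NNH = 100.0 (NNB = 75.2, NNH = 30.0) |
| 29% vs 30% | −0.0331, 0.0131 | NNB = 100.0 (NNH = 30.2, NNH = 76.5) | NNB = 100.0 (NNB = 30.2, NNH = 76.5) |
| 11% vs 10% | −0.0055, 0.0255 | NNH = 100.0 (NNH = 181.0, NNH = 39.2) | NNH = 100.0 (NNB = 181.0, NNH = 39.2) |

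The full set was 18 scenarios: placebo 10%, 30% or 50%; difference −1, 0 or +1 point; 1,500 or 3,000 per arm. Every interval crossed zero and every one printed two NNH limits. Of the six with a positive estimate, five put the estimate outside the printed limits. The sixth is the last row of the table.

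**The case against.** The strongest reply is that this is a typing slip whose intended meaning is plain. Rule 1 defines the negative side as NNB, rule 3 itself uses NNB for a negative estimate, the abbreviation list defines NNB, and SAP 8.1.1 has the two-label template. That is very probably right. It shows what the correction should be, but it does not remove the need for one, since the rule specifies output.

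A reader might infer more than the text supports:

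- *That a null result would look the same as significant harm.* It would not. Rule 2 prints its limits without labels and rule 3 prints labels inside the bracket. The same endpoints also have proportions with 95% intervals and a between-group comparison (Miettinen and Nurminen in 8.1.2.3, Fisher exact in Table 20), so the NNH line is not the only evidence.
- *That omitting the minus signs is the fault.* Rule 1 and the efficacy rule omit them too, without harm, because their labels carry the direction.
- *That most of these analyses will fall under rule 3.* About 95% would if there were no true difference, which is only the definition of a 95% interval. The documents give no reason to expect a null difference for either endpoint.
- *That the estimate always falls outside its printed limits.* This holds only for a positive estimate with |L| > d.

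**Conclusion.** Wrong as written, and minor. Whenever the interval for any local reaction or any systemic event includes zero, rule 3 labels the benefit-side limit as harm. A negative estimate then has an interval labelled entirely NNH, and a positive one can fall outside its own printed limits. The conclusion needs only the section's sign convention and rule 1; the rates and sample sizes above are assumptions used for illustration.

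The reach is one row of Table 20, covering two descriptive summaries. No confidence interval, test, endpoint definition or efficacy result changes. The documents do not support reading this as an error in the safety analysis itself.

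**What to change.** In rule 3 of SAP 8.1.2.3, change the bracket to (NNB = xx.x, NNH = xx.x), leave the rest of the sentence as it is, and carry the same label into the table shell. This matches the pattern of SAP 8.1.1. The cost is one label in two places, with no re-analysis.

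Two additions would be reasonable but are separate from this defect: showing the risk difference and its interval beside the NNH, and adding a rule for a difference of exactly zero, which 8.1.1 has and 8.1.2.3 lacks.

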#### **8.1.2.4. Concomitant Medications, Vaccinations, and Blood Products**

Antibiotics and systemic steroids will be summarized over 3 intervals:

1. The day of vaccination until the day before surgery, inclusive
2. The day of surgery until study completion (or dropout or withdrawal), inclusive
3. The day of vaccination until study completion (or dropout or withdrawal), inclusive

Intraspinal steroids will be summarized over 2 intervals:

1. 6 Months before study enrollment until the day before vaccination
2. The day of vaccination until completion of study participation

Nonstudy vaccines will be summarized over 2 intervals:

1. 6 Months before study enrollment until the day before vaccination
2. The day of vaccination until completion of study participation

Subjects will be counted once for each product in each interval. A subject will be included in the specified interval if either the start date or the stop date is contained in the interval.

Antibiotics, systemic steroids, intraspinal steroids, and nonstudy vaccines will be compared using the Fisher exact test, 2-sided.

Days of antibiotic use will be summarized over the same 3 intervals as antibiotics and systemic steroids. Any antibiotic uses that start before surgery and end after surgery will be split into 2 segments: the start of use until the day before surgery and the day of surgery to the end of use. The statistical test will be van Elteren, with site as a classification variable.

Use of blood products will be summarized over 3 intervals:

1. The day of vaccination until before surgery
2. Days 1-7 (where Day 1 is the day of surgery)
3. Days 8 or more

Use of blood products will be summarized as follows in each interval:

- Numbers and proportions of subjects receiving at least 1 transfusion will be compiled by vaccine group. The denominator will be the number of subjects in the time interval, ie, whose date of completion, dropout, or withdrawal is on or after the last day of the interval. The statistical test will be the Cochran-Mantel-Haenszel (CMH) test.
- The number of units will be summarized by n, mean, standard deviation, minimum, and maximum. Units will be obtained as the sum of all units received in the indicated interval. Vaccine groups will be compared using the van Elteren test, 2-sided. Only subjects receiving at least 1 transfusion will be included.
- Counts of transfusions per subjects (values 0, 1, 2, etc) will be compiled by vaccine group. Vaccine groups will be compared using the van Elteren test, 2-sided.
- Counts of transfusions will be further split by types of transfusions, also compiled by vaccine group. The types of transfusions will be packed RBCs, platelets, whole blood, plasma, and other. The denominator will be the number of subjects in the time interval. The statistical test will be the CMH test, 2-sided.
- Numbers and proportions of subjects receiving heterologous donation or autologous transfusions will be compiled by vaccine group. The denominator will be the number of subjects receiving packed RBCs or whole blood. The statistical test will be the CMH test, 2-sided.
- Numbers and proportions of subjects using cell saver will be compiled by vaccine group. The statistical test will be the Fisher exact test, 2-sided. Only subjects receiving at least 1 transfusion will be included.

All CMH tests will use site as a stratification factor.

Subjects who have more than 1 transfusion in the specified interval will not be counted more than once for any given category (eg, platelets), but will be counted for each separate category (eg, platelets for one transfusion and whole blood for a different transfusion).

Statistical analyses are summarized in [Section 8.2.2.4](#).

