5.4. Concomitant Medication(s), Vaccinations, and Blood Products

The following concomitant medications, vaccinations, and blood products will be recorded in the CRF:

- Antibiotics, including all antibiotic use from study enrollment until completion of study participation, start and stop dates, name of antibiotic, dose, route, and frequency.
- Systemic steroids, from study enrollment until completion of study participation, start and stop dates, medication name, dose, units, route, frequency, and indication for use.
- Intraspinal steroids, from 6 months prior to study enrollment until completion of study participation, including medication name and date administered.
- Nonstudy vaccines administered from 6 months prior to study enrollment until completion of study participation, including name of vaccine and date administered.
- Blood products, including number of units and type (eg, whole blood, red blood cells, platelets, clotting factors, cryoprecipitate, white blood cells, immunoglobulins, albumin, and plasma). In addition, whole blood and red blood cells should be identified as heterologous or autologous donations. If a cell saver is used to return the subject's red blood cells during the index surgical procedure, this information will be recorded. All blood product use should be recorded from study vaccination through study completion.

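### The interval rule for antibiotic and systemic steroid use tests end dates, not overlap, so a course that covers a whole interval is left out of that interval's subject count

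*SAP*

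**What the plan says.** SAP 8.1.2.4 summarizes antibiotics and systemic steroids over three intervals:

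- Interval 1: "The day of vaccination until the day before surgery, inclusive".
- Interval 2: "The day of surgery until study completion (or dropout or withdrawal), inclusive".
- Interval 3: "The day of vaccination until study completion (or dropout or withdrawal), inclusive".

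Subjects are counted once per product per interval, and membership follows one sentence: "A subject will be included in the specified interval if either the start date or the stop date is contained in the interval". The counts are then tested: "Antibiotics, systemic steroids, intraspinal steroids, and nonstudy vaccines will be compared using the Fisher exact test, 2-sided".

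The next paragraph of the same section deals with days of antibiotic use and adds a split: "Any antibiotic uses that start before surgery and end after surgery will be split into 2 segments". The first segment ends the day before surgery and the second begins on the day of surgery. This is not said to apply to the subject counts, and nothing like it is given for steroids. SAP Table 21 repeats the intervals without changing the rule. SAP Section 7 says that missing safety values are not imputed.

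On data collection, Protocol 5.4 asks for "Antibiotics, including all antibiotic use from study enrollment until completion of study participation, start and stop dates" and for "Systemic steroids, from study enrollment until completion of study participation, start and stop dates". Intraspinal steroids and nonstudy vaccines are recorded by date of administration only.

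**The concern.** A subject is exposed during an interval when the course overlaps it. A course that begins before the interval and ends after it, or has no stop date because it is still running, has neither date inside. The subject is then treated as a non-user of that product for a period in which it was taken every day. The omission is systematic, because only courses long enough to cover an interval can be lost.

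It can also make two rows of Table 21 disagree. Take an antibiotic that runs from before vaccination until after surgery. Under the split it contributes preoperative days of use, while under the count rule the same subject is not a preoperative user of that product.

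What is at stake is the accuracy of a supportive safety summary and of the Fisher comparisons built on it.

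**Working it through.** There is no planned figure to reproduce; the check is one of logic.

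**Set-up.** Let vaccination be day 0 and surgery day S, with S = 10 or 60, the ends of the protocol window. Surgery is study Day 1, so postoperative Day 180 is C = S + 179, which gives 189 or 239. The intervals are 1 = [0, S − 1], 2 = [S, C] and 3 = [0, C]. A course has start s and stop e, with e absent if the course is ongoing.

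**Rules compared**, for an interval [a, b]:

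- As written: a ≤ s ≤ b, or a ≤ e ≤ b.
- Overlap: s ≤ b, and e ≥ a or ongoing.

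The two differ exactly when s < a and the course ends after b or is ongoing. Interval 3 is the union of intervals 1 and 2, so it cannot recover a course that spans the whole study.

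**Results.** The assignments are the same for S = 10 and S = 60.

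| Course | As written | Overlap |
|---|---|---|
| Start before vaccination, ongoing | none | 1, 2, 3 |
| Start before vaccination, stop after completion | none | 1, 2, 3 |
| Start before vaccination, stop preoperatively | 1, 3 | 1, 3 |
| Start before vaccination, stop postoperatively | 2, 3 | 1, 2, 3 |
| Start preoperatively, stop postoperatively | 1, 2, 3 | 1, 2, 3 |
| Start preoperatively, ongoing at completion | 1, 3 | 1, 2, 3 |
| Start postoperatively, ongoing | 2, 3 | 2, 3 |
| Start and stop preoperatively | 1, 3 | 1, 3 |
| Day of surgery only | 2, 3 | 2, 3 |

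A worked case with S = 10: let s = −30 and e = 40. Interval 1 is [0, 9]. Neither −30 nor 40 lies in it, so the subject is not counted, although the course covers all ten days.

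Four of the nine patterns are misassigned, and two of the four fall in no interval. If the split at surgery were also applied to the subject counts, and to steroids, all nine would be assigned correctly. The SAP does not say that it is.

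**Dependence on how dates are recorded.** Take a course begun before vaccination and ongoing at completion:

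- Start recorded as the day of vaccination (s = 0), no stop date: counted in 1 and 3, missed in 2.
- True start kept, stop set to completion (e = C): counted in 2 and 3, missed in 1.
- Both conventions: counted in 1, 2 and 3.
- Neither convention: counted in none.

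The documents state neither convention.

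**Can such courses occur?** Protocol 5.4.1 generally permits medication for stable preexisting conditions. The steroid criteria in Protocol 4.2 (exclusion 7) and 4.3 apply from 10 mg/day of prednisone or equivalent, so that threshold does not catch lower-dose long-term use. The antibiotic delay criterion in 4.3 concerns acute illness only. Exclusion 7 also bars illness that requires chronic treatment with known immunosuppressants. The patterns are possible but should be uncommon.

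**The case against.** The strongest reply has five parts.

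- **The split at surgery already handles antibiotics.** It does so for days of use. It sits in that paragraph and does not mention the Fisher counts or steroids. The objection narrows the point to the subject counts but does not remove it.
- **The case of being counted nowhere depends on case report form conventions that the documents do not show.** This stands. It needs a recorded start before vaccination together with a stop that is missing or after completion. If starts were recorded from the day of vaccination and open courses were closed at completion, the rule would count every pattern correctly. Protocol 5.4 collects use from enrollment onward but does not say how an earlier start is entered.
- **Counting is per product.** This also stands. A long-term antibiotic user who receives a different antibiotic as surgical prophylaxis is counted in intervals 2 and 3 for that product. Only the long-term product is missed.
- **Nothing depends on the table.** No covariates enter the primary or secondary efficacy analyses (SAP 6.4), and systemic steroid use is not a listed term in the immunogenicity models (SAP 8.1.3.5). The same rule applies to both groups, and use begun before vaccination should be balanced by randomization. This holds, and it sets the priority.
- **Treating every missing stop date as ongoing would create a new error.** A short course with a lost stop date would be carried into every later interval. This is right, and the fix has to allow for it.

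A reader might also infer that the courses lost are those most able to alter immune response. The documents do not support that: the eligibility and delay criteria remove much of the higher-dose steroid use around vaccination. Nor does the fact that every course covering an interval can be missed say how many subjects have one.

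**Conclusion.** Read as written, the sentence gives wrong subject counts for antibiotics and systemic steroids whenever a course covers a whole interval, and no other text in the protocol or SAP corrects it. This is a faulty rule and not merely a missing detail.

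Its reach is limited. Two of the four medication classes under the Fisher tests, intraspinal steroids and nonstudy vaccines, have single dates and are unaffected. The number of subjects concerned is not stated and is probably small. The consequence is undercounted use in a supportive safety table. A bias between groups is not shown, and no efficacy conclusion is touched.

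The conclusion that some courses are missed in all three intervals assumes that true start dates before vaccination are recorded and that ongoing courses are not closed at completion. The single-interval omissions need only one of those conditions: the first for interval 1, the second for interval 2.

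Label: wrong as written, low priority.

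**What to change.** Replace the inclusion sentence in SAP 8.1.2.4 with an overlap rule. A subject is counted in an interval if the course starts on or before the interval's last day and either stops on or after its first day or is flagged as ongoing. A flagged course is carried to completion, dropout or withdrawal. State separately how a course is treated when its stop date is unknown and it is not flagged as ongoing, for example by listing it and counting it only in the interval that contains its start.

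Add that the split at surgery is for computing days of antibiotic use, so that the two rows of Table 21 follow consistent definitions.

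The cost is two or three sentences in the SAP and a small programming change. Start and stop dates are already collected under Protocol 5.4. The documents do not say whether an ongoing flag exists for these medications; that should be confirmed before programming. No conduct of the trial changes.
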